#### **5.2.2 Procedures for handling subjects incorrectly enrolled or randomized**

Participants incorrectly enrolled in the study will be followed till the study end. They will remain in the group they were randomized to. Participants with contraindications to a specific study medication will have that drug discontinued. Participants incorrectly started in the wrong group (i.e. to which they were not allocated) will be switched to the correct treatment group.

### **5.3 Interventions and monitoring**

#### **5.3.1 Intensive metabolic intervention (induction phase of the trial)**

An intensive metabolic intervention will be used in intervention group participants for induction of a normoglycemic state. It will be 12 weeks in duration and will include intensive lifestyle therapy and intensive treatment with Forxiga, metformin and insulin glargine. Participants will be asked to discontinue all other glucose-lowering medications.

### **5.3.1.1 Treatment with and handling of Forxiga**

Participants randomized to the intervention group will be started on Forxiga 5 mg po daily for 4 days and then the dose will be increased to 10 mg po daily. Participants will be continued on this dose for 12 weeks. Forxiga will be manufactured and shipped by AstraZeneca. Labels will be prepared in accordance with Good Manufacturing Practice and local regulatory guidelines for labeling. The drug will be stored at room temperature (15-30°C) in accordance with the storage conditions specified on the package label. Creatinine will be checked 2 weeks after drug initiation, and then monthly during the intensive metabolic intervention. Forxiga will be permanently discontinued if eGFR falls to  $<60 \text{ mL/min/1.73m}^2$ . Forxiga contains lactose and may cause abdominal discomfort in lactose-intolerant individuals. Forxiga will be temporarily stopped or permanently discontinued if a participant develops side effects.

### **5.3.1.2 Titration of other glucose-lowering medications**

In drug-naive patients, metformin 500 mg po (orally) once daily (OD) will be administered for 4 days, then increased to 500 mg po twice daily (bid) for 4 days, then 1,000 mg po bid. Patients already on metformin will be continued on it with further titration to maximal tolerated doses.

At randomization, participants will be concurrently started on insulin glargine 2-6 units sc (subcutaneously) at bedtime, and the dose will be titrated by the participant with guidance from the research team aiming to achieve a fasting glucose of 4.0-5.3 mmol/L on self-monitoring of capillary blood glucose (SMBG). Insulin glargine is chosen in view of the previous experience of our center in using this insulin analogue to achieve similar glycemic targets in patients with early type 2 diabetes and prediabetes in the ORIGIN trial, a multicenter randomized controlled trial with more than 12,500 participants. The overall goal will be to finish medication titration by the end of week 2, and to maintain the fasting glycemic target of 4.0-5.3 mmol/L for the remaining duration of the intensive metabolic intervention. No other glucose-lowering medications apart from insulin glargine, metformin and Forxiga will be used in intervention group participants during the intensive metabolic intervention. All study drugs will be kept in a secure place under appropriate storage conditions.

### **5.3.1.3 Intensive lifestyle intervention**

The overall goals of the intensive lifestyle intervention are to achieve and maintain  $\geq 150$  min of moderate physical activity per week by week 12 and  $\geq 5\%$  reduction in baseline weight by week 24 of the trial. These goals might be modified depending on participant's baseline weight and physical ability. At baseline, participants randomized to the intervention group will meet with research staff who will prescribe a personalized low-calorie diet and a moderate-intensity exercise program based on participant's current physical activity patterns and cardiovascular history. Participants will be provided with a pedometer as an incentive to engage in physical activity. Participants in the intervention group will meet with research personnel every 1-2 weeks during the intensive metabolic intervention period for goal reinforcement, behaviour modification and problem-solving.

#### **5.3.1.4 Monitoring during the induction phase of the trial**

At the first study visit, intervention group participants will be taught how to self-monitor capillary blood glucose and how to inject insulin. Participants and their families will also be taught how to recognize and treat hypoglycemia. During the intensive metabolic intervention, participants will be asked to monitor glucose at least twice daily at varying times, including before and 2 hours after meals, and during exercise. Research staff will meet with intervention group participants once a week during the first 6 weeks of the trial and will contact them by telephone at least once a week between visits to review glucose readings, medication titration, medication adherence and side effects (see schedule in Table 1 in Appendix A). Research staff will continue to meet with intervention group participants every 2 weeks and will contact them by telephone every other week during week 7-12 of the trial. All hypoglycemic episodes will be documented and reviewed with an investigator promptly. Glucose-lowering therapy will be adjusted accordingly.

#### **5.3.2 Control group follow-up during the induction phase of the trial**

Participants assigned to the standard diabetes therapy group will meet with research personnel at the beginning of the trial who will review self-monitoring of capillary blood glucose, management of hypoglycemia, and the importance of healthy diet and regular exercise in diabetes management. Control group participants will also be provided with a pedometer as an incentive to be active. Glucose levels in standard group participants will be managed by their regular diabetes care provider according to the current Canadian Diabetes Association (CDA) Clinical Practice guidelines. Any approved glucose-lowering medication will be allowed in the control group.

#### **5.3.3 Monitoring for hyperglycemia relapse during the maintenance phase of the trial**

In all participants, HbA1C will be drawn during week 12 of the trial. At the end of week 12, glucose-lowering medications will be discontinued in all participants with a HbA1C <7.3%, and insulin will be tapered over a 5-day period. Participants will be encouraged to continue with lifestyle modifications and regular home glucose monitoring (i.e. at least 5 fasting capillary measures per week). They will meet with research staff every 2-4 months during the maintenance phase of the trial to review any challenges in achieving and maintaining exercise and weight loss goals. Participants will be assessed by research staff every 1-2 months by telephone to review adherence to lifestyle therapy, SMBG readings and to screen for symptoms of hyperglycemia.

It is possible that glucose levels may quickly rise after glucose-lowering drugs are stopped in some of the participants whose HbA1C is <7.3% on these drugs. This rise may not be detected with HbA1C levels due to the well-known time-lag between rising glucose levels and rising HbA1C levels.

In light of the above, hyperglycemia relapse will be defined as follows:

- a. a HbA1C  $\geq$  7.0% at 24, 36, 48 and 64 weeks; or
- b. reinitiation of glucose-lowering drugs; or

- c. capillary glucose values  $\geq 10$  mmol/L on  $\geq 50\%$  of SMBG readings over 1 week in the absence of an acute illness.

All participants identified to have hyperglycemia relapse will receive standard glycemic management according to the judgment of their physician or investigator. Participants found to have HbA1C  $\geq 7.3\%$  on therapy during week 12 of the trial will also receive standard glycemic management. These participants will continue to be contacted by telephone every 1-2 months to review SMBG readings, medication adherence and side effects.

## **5.4 Methodological considerations**

### **5.4.1 Planned recruitment**

A total of 152 participants will be enrolled in this trial. Participants will be recruited at approximately 7 Canadian sites. Based on our experience in the pilot trial, we anticipate an average recruitment rate of 2 participants per month at each site. Total trial duration is estimated to be 2.5 years based on a 3-month start-up period, 12-month recruitment period and 15-month follow-up period. If recruitment rates fall behind schedule, we will expand the trial to additional sites. The trial will be coordinated through the Population Health Research Institute which has an extensive experience in conducting multicentre randomized controlled trials (RCT) and offers a large pool of experienced research personnel.

### **5.4.2 Treatment adherence**

Adherence to intensive lifestyle and glucose-lowering therapy for participants in the intervention group will be encouraged during frequent clinic visits and telephone follow-ups. It will also be promoted by prompt attention to any side effects of the medications and the short, 12-week duration of the intervention period.

Medication adherence will be measured by inspecting medications at each study visit. Additionally, two six-point glucose profiles will be collected during the 6th and 12th week after randomization. Each six-point glucose profile will include pre-meal and 2-hour post-meal SMBG measurements taken on the same day. Adherence to lifestyle advice in both treatment groups will be measured by a physical activity questionnaire and food frequency questionnaires administered at baseline, 12, 24, 36, 48 and 64 weeks after randomization. Anthropometric measurements at study visits will also reflect adherence to the lifestyle intervention.

### **5.4.3 Losses to follow-up**

Losses to follow-up are expected to be minimal as the study duration is only 64 weeks. The investigators will make every effort to contact participants who are lost to follow-up. In order to minimize losses to follow-up, participants who do not adhere to the assigned treatment or visit schedule will be encouraged to do HbA1C measurements through their regular diabetes care provider and will be contacted by telephone to collect key data. Participants who withdraw consent will be asked to return any study drugs to the study centre and encouraged to return to their regular diabetes care provider for assessment and further care.

#### **5.4.4 Confidentiality and record retention**

Personal information of study participants will be kept in strict confidence. Participants' names will be removed from the data and replaced with identification numbers. The study investigator will keep a participant identification list (identification numbers with the corresponding participants names) in a secure location. Study data will be stored on a computer at the Population Health Research Institute in accordance with local data protection laws. The health records related to this study will be kept by each site for up to 25 years after the end of the trial.

## **6. COLLECTION OF STUDY VARIABLES**

### **6.1 Recording of data**

Study variables will be collected at enrollment and during follow-up according to the visit schedule (See Table 1 in Appendix A). Study data will be recorded on data collection forms and transmitted to the Population Health Research Institute (PHRI).

### **6.2 Study outcomes**

#### **6.2.1 Primary and secondary outcomes**

The primary outcome is drug-free diabetes remission, defined as a HbA1C < 6.5% without use of glucose-lowering agents for at least 12 weeks. Related outcomes to be analyzed include complete diabetes remission, defined as a HbA1C < 6.0% without use of glucose-lowering agents for at least 12 weeks, and diabetes regression, defined as a HbA1C of 6.5-6.9% without use of glucose-lowering agents for at least 12 weeks.

HbA1C will be measured in the local labs at 12, 24, 36, 48 and 64 weeks after randomization, during which use of glucose-lowering medications will also be ascertained. FPG will also be measured in the local lab at 16 weeks. All FPG levels will be measured approximately 48 hours after the last dose of any glucose-lowering medication unless fasting capillary glucose rises above 12 mmol/L.

#### **6.2.2 Other outcomes**

Symptomatic and severe hypoglycemic episodes will be measured in both treatment groups. Anthropometric measures including height (at the screening visit only), body weight, waist and hip circumference will be measured in all participants (see schedule in Appendix A Table 1). Body mass index will be reported in kg/m^2. Waist circumference will be measured around the exposed abdomen at the level of the top of the iliac crest at the end of a normal expiration. Hip circumference will be measured as the maximal circumference over the buttocks over light clothing.

In addition, 2 six-point glucose profiles will be collected during the 6th and 12th week after randomization. Each six-point glucose profile will include pre-meal and 2-hour post-meal readings taken on the same day. To standardize this measure, all participants will be provided with identical glucometers which will be calibrated regularly. Mean fasting and post-meal glucose values will be calculated for each participant from the two glucose profiles.

### 6.2.3 Stored blood

In addition to obtaining fasting serum samples at baseline, fasting serum samples will also be taken for storage at 16 weeks in participants who agree to it. They will be shipped and stored centrally. Genetic markers and analytes related to diabetes remission may be measured after the trial has finished.

## 6.3 Safety

### 6.3.1 Safety variables

Information on the following prespecified safety outcomes will be prospectively collected in all study participants during the trial:

- 1) Death (and cause of death as determined by a physician);
- 2) Non-fatal myocardial infarction or angina resulting in hospitalization or emergency room admission;
- 3) Non-fatal stroke or transient ischemic attack diagnosed by a physician;
- 4) Heart failure resulting in hospitalization or emergency room admission;
- 5) Resuscitated cardiac arrest or life-threatening arrhythmia (including documented or presumed ventricular fibrillation, sustained ventricular tachycardia, asystole, or pulseless electrical activity);
- 6) Cardiogenic shock diagnosed by a physician;
- 7) Diabetic ketoacidosis or hyperglycemic hyperosmolar state diagnosed by a physician;
- 8) Documented new fractures;
- 9) Newly diagnosed cancers;
- 10) Genitourinary infections diagnosed by a physician;
- 11) Moderate (eGFR 30-60 mL/min/1.73 m^2 by MDRD formula) or severe (eGFR <30 mL/min/1.73 m^2) renal dysfunction;
- 12) Symptomatic and severe hypoglycemic events (see below for definitions);
- 13) Hospital or emergency room admissions (and reasons for admission).

Participants will be asked to record all hypoglycemic episodes and symptoms in a diary that will be provided to them. Moreover, they will be explicitly asked about any episodes of symptomatic or severe hypoglycemia during every visit and telephone follow-up.

*Symptomatic hypoglycemia* is defined as an event with clinical symptoms consistent with hypoglycemia, based on data recorded in the participant's diary. These will be further categorized as confirmed (i.e. with a concomitant home glucose reading  $\leq 3.0$  mmol/L) or unconfirmed. Symptomatic hypoglycemic events and those that result in alteration of any of the study drugs will be recorded.

*Severe hypoglycemia* is defined as an event with clinical symptoms consistent with hypoglycemia in which the participant required the assistance of another person, and one of the following: (i) the event was associated with a documented self-measured or laboratory plasma glucose level  $\leq 2.0$  mmol/L; or (ii) the event was associated with prompt recovery after oral carbohydrate, intravenous glucose, or glucagon administration. Any episode of severe hypoglycemia will be recorded and reviewed within one working day.

All safety variables will be recorded on case report forms and supporting documentation will be obtained. Information on adverse events and pregnancies will be collected as described in Sections 6.3.2-6.3.5. The investigators will review safety data for this open trial monthly and more formally after the first 50 patients have completed the trial to determine if any modifications to the protocol are indicated.

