### **6.3.2 Definitions of adverse events**

#### **6.3.2.1 Adverse events**

An adverse event is any untoward medical occurrence that occurs in a person during the period of observation in a clinical study. It does not necessarily have to have a causal relationship with any treatment administered as part of that study. An adverse event can therefore be any unfavorable and unintended sign, symptom or disease, whether or not it is considered related to any medicinal product being taken at the time the event occurs.

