### **6.3.3 Documentation and reporting of adverse events, pregnancies and overdoses**

#### **6.3.3.1 Documentation and reporting of non-serious adverse events**

Any adverse event resulting in a change in dose (including temporary withholding) of any of the study medications (insulin glargine, metformin and Forxiga) will be documented on case report forms. Examples of such events could include gastrointestinal complaints or genitourinary infections. All changes in the medication dose will be recorded.

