### **6.3.5 Period of observation**

For the purposes of this study, the period of observation for collection of adverse events, SAEs, overdoses and any pregnancies extends from the time the participant gives informed consent until the end of the study.

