### 13. APPENDIX A

**Table 1.** Schedule of visits and assessments in the intervention group (I), control group (C), and both groups (X).

	Weeks after randomization																			
	-1	0	0.5	1	1.5	2	2.5	3	3.5	4	4.5	5	5.5	6	7	8	9	10	11	12
Eligibility criteria	X																			
Informed consent	X																			
Randomization		X																		
Start study medications		I																		
Stop diabetes medications																				X
Clinic visit	X	X		I		I		I		I		I		X		I		I		X
Telephone follow-up			I		I		I		I		I		I		I		I		I	
Adherence to medications and side effects			I	I	I	I	I	I	I	I	I	I	I	X	I	I	I	I	I	X
Review SMBGs			I	I	I	I	I	I	I	I	I	I	I	X	I	I	I	I	I	X
Height	X																			
Weight	X	X						I						X		I		I		X
Waist and Hip Circumference		X												X						X
Blood pressure	X	X		I		I		I		I		I		X		I		I		X
Physical activity and food frequency questionnaires*	X																			X
ECG	X																			
Fasting serum for storage**	X																			
FPG	X																			
Serum ALT	X																			
Serum creatinine	X					I								I				I		
Urine BhCG***	X																			
HbA1C	X																			X
Two glucose profiles****														X						X
Return to standard glycemic care if hyperglycemia relapse identified																				
AE/SAE Review and Reporting			X	X	X	X	X	X	X	X	X	X	X	X	X	X	X	X	X	X

\*A quality of life questionnaire will also be administered at -1, 12 and 64 weeks.

\*\*Fasting serum sample will be taken for storage during the screening visit and at 16 weeks.

\*\*\*Urine BhCG will be measured in women with childbearing potential.

\*\*\*\* Two six-point glucose profiles will be collected on separate days. Each six-point glucose profile will include pre-meal and 2-hour post-meal SMBG readings taken on the same day.

	Weeks after randomization													
	12.5	16	20	24	28	32	36	40	44	48	52	56	60	64
Eligibility criteria														
Informed consent														
Randomization														
Start study medications														
Stop diabetes medications														
Clinic visit		X		X			X			X				X
Telephone follow-up	X		X		X	X		X	X		X	X	X	
Adherence to medications and side effects	X	X	X	X	X	X	X	X	X	X	X	X	X	X
Review SMBGs	X	X	X	X	X	X	X	X	X	X	X	X	X	X
Height														
Weight		X		X			X			X				X
Waist and Hip Circumference		X		X			X			X				X
Blood pressure		X		X			X			X				X
Physical activity and food frequency questionnaires*				X			X			X				X
ECG														
Fasting serum for storage**		X												

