FPG		X												
Serum ALT		X												X
Serum creatinine		X												X
Urine BhCG***														
HbA1C				X			X			X				X
Two glucose profiles****														
Return to standard glycemic care if hyperglycemia relapse identified	X	X	X	X	X	X	X	X	X	X	X	X	X	X
AE/SAE Review and Reporting	X	X	X	X	X	X	X	X	X	X	X	X	X	X

\*A quality of life questionnaire will also be administered at -1, 12 and 64 weeks.

\*\*Fasting serum sample will be taken for storage during the screening visit and at 16 weeks.

\*\*\*Urine BhCG will be measured in women with childbearing potential.

\*\*\*\* Two six-point glucose profiles will be collected on separate days. Each six-point glucose profile will include pre-meal and 2-hour post-meal SMBG readings taken on the same day.

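### Non-serious hypotension and volume depletion are not listed safety outcomes, and the only stated recording rule for non-serious events depends on a study-drug dose change, so even capture in the two arms is not secured

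*Combined protocol and SAP*

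**What the plan says.** Section 6.3.1 introduces its list of 13 safety outcomes with "Information on the following prespecified safety outcomes will be prospectively collected in all study participants during the trial". The list covers death, cardiovascular events, ketoacidosis, fractures, cancers, genitourinary infections, renal dysfunction, hypoglycemia, and admissions to hospital or the emergency room with their reasons. Hypotension and volume depletion are absent. Exclusion criterion 9 in section 4.2 bars entry to patients with either, and sets the hypotension threshold at a systolic pressure below 90 mmHg.

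For other events, 6.3.1 points onward: "Information on adverse events and pregnancies will be collected as described in Sections 6.3.2-6.3.5". In those sections:

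- 6.3.2.1 defines an adverse event broadly, as "any unfavorable and unintended sign, symptom or disease" whether or not it is thought to be drug-related.
- 6.3.3.1 gives the rule for non-serious events: "Any adverse event resulting in a change in dose (including temporary withholding) of any of the study medications" is documented on case report forms. The drugs named are insulin glargine, metformin and Forxiga.
- 6.3.3.2 requires a form for every serious adverse event.
- 6.3.5 sets the window: "the period of observation for collection of adverse events, SAEs, overdoses and any pregnancies extends from the time the participant gives informed consent" to the end of the study.

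Table 1 in Appendix A has a row "AE/SAE Review and Reporting", marked for both groups in every column after randomization. It also has a row "Adherence to medications and side effects", marked for both groups at weeks 6 and 12 but for the intervention group alone at the other induction contacts. Hypoglycemia gets firmer treatment: participants keep a diary and, under 6.3.1, "they will be explicitly asked about any episodes of symptomatic or severe hypoglycemia during every visit and telephone follow-up".

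**The concern.** The plan treats low blood pressure and volume depletion as a reason not to enroll someone, but does not say how non-serious cases are to be counted afterwards. The case at issue is mild: a symptomatic episode between visits, handled with fluids or a change of blood pressure drug, with no admission and no change to a study drug. Under the stated rule, whether it reaches a case report form depends partly on which drugs the participant takes and how often staff make contact. Both differ by arm.

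A blood pressure reading can be summarised later. An episode that nobody wrote down cannot be recovered. If the intervention arm shows more recorded episodes, the team could not tell more harm from better capture. A dizzy spell without a glucose reading might also be filed as unconfirmed symptomatic hypoglycemia, which 6.3.1 defines by symptoms noted in the diary, and hypoglycemia is the trial's stated safety objective (2.3).

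**Working it through.** The plan gives no figure on this point to reproduce. The check compares sections and counts the schedule.

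**1. Who can trigger the recording rule.** In the intervention arm everyone starts Forxiga and glargine, and starts or continues metformin (5.3.1.1, 5.3.1.2). Forxiga is stopped, temporarily or for good, if side effects develop, and that meets the 6.3.3.1 condition. Controls may have entered on no glucose-lowering drug (4.1, criterion 4) and may take any approved agent (5.3.2). Those on metformin or glargine can trigger the rule; those on none of the three drugs cannot. Control capture is therefore lower under a literal reading, but not zero.

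**2. Scheduled contacts, weeks 0.5 to 12 (Table 1, 18 columns).**

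- Intervention visits at weeks 1, 2, 3, 4, 5, 6, 8, 10, 12 = 9.
- Intervention calls at weeks 0.5, 1.5, 2.5, 3.5, 4.5, 5.5, 7, 9, 11 = 9. Total 9 + 9 = 18.
- Control visits at weeks 6 and 12 = 2, with no calls.
- Intervention-only contacts: 18 − 2 = 16.
- Blood pressure visits in the same period: 9 v 2.

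**3. Time since the previous scheduled contact.**

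- Week 6: intervention 6 − 5.5 = 0.5 week; control 6 − 0 = 6 weeks.
- Week 12: intervention 12 − 11 = 1 week; control 12 − 6 = 6 weeks.

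**4. What is captured in both arms already.** Serious events (6.3.3.2), admissions with reasons (6.3.1, item 13), and blood pressure at the seven shared visits after randomization: weeks 6, 12, 16, 24, 36, 48 and 64.

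**5. Illustration of unequal capture.** With the same true risk p in both arms, false difference = p × (capture in intervention − capture in control). The documents give neither p nor the capture rates, so all values here are assumed, with 76 per arm (11.1).

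| True risk | Capture, intervention v control | False difference |
|---|---|---|
| 5% | 90% v 90% | 0 |
| 2% | 90% v 70% | 0.02 × 0.2 = 0.4 points |
| 5% | 90% v 50% | 0.05 × 0.4 = 2.0 points |
| 10% | 90% v 30% | 0.10 × 0.6 = 6.0 points |
| 15% | 90% v 20% | 0.15 × 0.7 = 10.5 points |

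In the third row the expected recorded counts are 76 × 0.05 × 0.9 = 3.4 and 76 × 0.05 × 0.5 = 1.9, a gap of 1.5 episodes. The spread from 0 to 10.5 points shows that the size depends on the assumptions.

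**6. Precision of the proposed table, 76 per arm all attending.**

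- 0 of 76: Clopper-Pearson upper 95% limit 1 − 0.025^(1/76) = 4.7%.
- Newcombe 95% intervals for the risk difference: 0 v 0 gives 0 (−4.8 to 4.8) points; 3 v 0 gives 3.9 (−1.5 to 11.0); 5 v 0 gives 6.6 (0.5 to 14.5).
- Baseline-adjusted systolic difference, half-width = 1.96 × SD × √(2/76) × √(1 − r²). With assumed SD 15 mmHg and r = 0.5 this is 4.1 mmHg; SD 12 with r = 0.7 gives 2.7, and SD 18 with r = 0.5 gives 5.0.

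**The case against.** The strongest reply is that this reads too much into silence. Section 6.3.3.1 says that dose-change events are documented; it does not say that no others are. The broad definition in 6.3.2.1, the window in 6.3.5 that names adverse events separately from serious ones, and the both-group review row in Table 1 can fairly be read together as general collection. The case report forms are not available, and section 10 leaves data procedures to a data management plan. This much stands: a reader might infer that mild episodes will go unrecorded, or that only dose-change events are kept, and the documents do not show either. They show only that no other recording rule is stated. The review row names no criterion, and 16 of its 18 induction columns have no scheduled control contact behind them.

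It can also be said that uneven contact is inherent in an open-label intensive intervention and affects every event type, and that an entry exclusion does not by itself require a matching outcome: polycythemia and raised ALT are also exclusions without a listed outcome. Both points are fair. They are reasons to keep the point minor and to amend the recording rule as well as the list. Investigators do review safety data monthly, and more formally after 50 participants have completed (6.3.1), but they can review only what was recorded.

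Last, the fix does not remove all imbalance, and the blood pressure readings are scheduled anyway. That is correct. Only the elicited-episode count adds new data, and it stays open to more frequent prompting and shorter recall in the intervention arm.

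**Conclusion.** The concern holds in a limited form. As written, the plan does not secure even capture of non-serious symptomatic hypotension or volume depletion when no study-drug dose changes, and a literal use of 6.3.3.1 would favour capture in the intervention arm. This rests on reading 6.3.3.1 as the operative rule and on the Table 1 contact rows (18 v 2).

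A reader might go further and take 18 v 2 as a measure of bias, or conclude that the safety comparison as a whole is unreliable. The documents support neither. They give no event rate or capture rate, so the false difference cannot be estimated and could be zero. Serious episodes, admissions, blood pressure at shared visits and the primary analysis are unaffected. This is a minor, inexpensive improvement.

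**What to change.** - **6.3.1:** add symptomatic hypotension or volume depletion, with a short definition, and systolic pressure below 90 mmHg.
- **6.3.3.1:** state that listed safety events are recorded in both arms whether or not a study-drug dose changes.
- **Elicitation:** ask one identical question with the same look-back (since the last shared visit) in both arms at weeks 6, 12, 16, 24, 36, 48 and 64. The hypoglycemia question in 6.3.1 is the model.
- **11.2:** for weeks 6 and 12, report per arm the number and percent with systolic below 90 mmHg, and the number and percent with an elicited episode, each with a risk difference and 95% CI. Use shared visits only. Show readings and reports from intervention-only contacts within that arm, without comparison.
- **Caveat to state:** more frequent prompting and shorter recall in the intervention arm leave some imbalance in the elicited count; the systolic count does not depend on recall.
- **Optional:** the baseline-adjusted blood pressure difference, labelled descriptive. A fall may be a benefit, since entry allows systolic pressure up to 180 mmHg and the lifestyle goal is at least 5% weight loss.

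The cost is one question at seven existing visits and a few lines of text, with no new visit or measurement. The downside is one more safety table, probably with few events and wide intervals. Other unlisted non-serious events would still fall under the dose-change rule.
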